# 7.1.2.2.2 Dosage, Administration, and Schedule

Lenalidomide will be taken once-daily orally at a dose of 25 mg on days 1-21 of each 28-day cycle. Lenalidomide should be taken at home by the subject at about the same time each day. Lenalidomide capsules should be swallowed whole with water. The capsules should not be opened, broken, or chewed. If a planned dose is missed, it should be taken as soon as possible within the same calendar day and with a return to the regular schedule the following day. If a planned dose is missed for more than a calendar day, subjects should not make up doses, but should resume the dosing regimen on schedule with the next cycle. Dose modifications are permitted in response to toxicity following the dose modification guideline tables.

The planned dose, quantity administered, start date, start time, and reason for dose change are to be recorded on each subject's eCRF.

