#### 7.4 Dose Modification

# 7.4.1 Dosage Adjustments, Delays, Rules for Withholding or Restarting, Permanent Discontinuation

# 7.4.1.1 Amgen Investigational Product: Carfilzomib

The reason for dose change of carfilzomib is to be recorded on each subject's CRF.

Carfilzomib may be discontinued, temporarily delayed, or dosage temporarily reduced, in the event of a treatment-related toxicity that, in the opinion of the investigator, warrants the discontinuation, temporary delay or dose reduction. Carfilzomib dose must be modified based on specified toxicities, as indicated in Table 7-3 and Table 7-4. The subject will be considered on protocol treatment while receiving carfilzomib. Carfilzomib (both twice-weekly and once-weekly regimen) must be discontinued permanently if a delay of more than 6 weeks is required due to unresolved toxicity.

If day 1 of a cycle is delayed, day 1 of subsequent cycles should be adjusted accordingly to maintain the 28-day cycle duration. However, if a within-cycle dose is delayed, then the dates of the subsequent within-cycle doses should not be adjusted.

Protocol Number: 20170596

**Date**: 20 May 2019 Page 58 of 132

If carfilzomib administration does not commence within the allowable window of the scheduled administration date, then the dose will be considered a missed dose. Administration may resume at the next planned dosing date. A missed dose will not be made up.

If either carfilzomib or dexamethasone are held for the remainder of the previous cycle or the new cycle is delayed due to residual toxicity on the planned day 1 of the next cycle, then the new cycle will be started at 1 dose decrement for the drug(s) causing the delay.

For conditions that do not require carfilzomib dose reduction, refer to Section 7.4.1.3.

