# 7.6 Treatment Compliance

Administration of IV medicinal products will occur at the study site. Oral medicinal products may be dispensed for self-administration at home. Subjects are to document all administered doses and missed doses in a medication diary for all study-required medication taken at home.

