#### 10. Statistical Considerations

#### 10.1 Sample Size Determination

The study is descriptive in nature. Approximately 75 subjects will be enrolled in the study with approximately 25 subjects in each treatment arm.

The sample size is assessed in terms of the expected levels of precision for estimating the proportion of subjects completing 12 cycles of treatment, relative dose intensity (%), and incidence of adverse events.

With a sample size of 25 subjects for each treatment arm, assuming 50%, 75%, or 90% of subjects will complete 12 cycles of treatment, the expected half-widths of the 95% CI for estimating the proportion of subjects completing 12 cycles of treatment are calculated as below.

	95% Confidence Interval Half-width (%)		
Sample Size	50%	75%	90%
25	20.5	18.1	13.5

In the A.R.R.O.W. trial, the mean (standard deviation) of relative dose intensity of carfilzomib is 92.2 (11.2) in Once-weekly subjects. In this study with a sample size of 25 subjects in each treatment arm, assuming standard deviation ranges from 5% to 15%, the expected half-widths of the 95% CI for estimating the mean relative dose intensity are calculated as below.

	95% Confidence Interval Half-width (%)		
Sample Size	SD = 5	SD = 10	SD = 15
25	2.0	3.9	5.9

For subject incidence of adverse events of 1%, 5%, 10%, 50%, 80%, the expected half-widths of the 95% confidence interval (CI) for estimating the subject incidences of adverse events are calculated as below.

	95% Confidence Interval Half-width (%)				
Sample Size	1%	5%	10%	50%	80%
25	7.8	10.8	13.5	20.5	16.9

Protocol Number: 20170596

**Date:** 20 May 2019 Page 81 of 132

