**Date:** 20 May 2019 **Page 84 of 132** 

#### 10.3.2.3 Safety Analyses

#### 10.3.2.3.1 Analyses of Primary Safety Endpoint(s)

Endpoint	Statistical Analysis Methods
Primary	Unless otherwise specified, following analyses will be based on the safety analysis set. The analyses will be carried out for subjects on the Kd, KRd, and KPd regimens, respectively.
	The proportion of subjects completing 12 cycles of Kd, KRd, and KPd treatment will be calculated based on the safety analysis set.
	The proportion of actual cumulative dose received to the full intended cumulative dose in cycles 1-12 will be summarized descriptively. The full intended cumulative dose is defined as all therapy specified per Sections 7.1.1.2 and 7.1.2 without consideration for dose modification or skipped doses. Relative dose intensity in cycles 1-12 will be summarized descriptively. Dose modifications including dose reduction, dose withheld, and dose delay in cycles 1-12 will be summarized along with reasons including adverse events and non-adverse events. Treatment-emergent adverse events and serious adverse events in cycles 1-12 will be summarized descriptively following the methods specified in Section 10.3.2.3.
Secondary	Not applicable
Exploratory	Not applicable

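### After a short lapse, the lenalidomide and pomalidomide missed-dose rule stops the drug until the next cycle, and the forfeited doses lower the oral-drug cumulative dose proportion in KRd and KPd

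*Protocol*

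**What the plan says.** Protocol Section 7.1.2.2.2 (lenalidomide) deals with missed doses in two steps. For a planned dose remembered the same day, "it should be taken as soon as possible within the same calendar day and with a return to the regular schedule the following day". For a dose missed beyond that, the wording is "for more than a calendar day, subjects should not make up doses, but should resume the dosing regimen on schedule with the next cycle". Section 7.1.2.3.2 repeats both sentences for pomalidomide. No reason is given for waiting until the next cycle, and nothing elsewhere in the protocol softens the instruction.

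The carfilzomib rule in Section 7.4.1.1 is different. It says "A missed dose will not be made up", but also "Administration may resume at the next planned dosing date".

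Section 10.3.2.3.1 makes the ratio of actual to full intended cumulative dose over cycles 1-12 a primary endpoint: "The full intended cumulative dose is defined as all therapy specified per Sections 7.1.1.2 and 7.1.2 without consideration for dose modification or skipped doses". Section 7.1.2 includes both oral drugs.

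Three places bear on what is recorded and reported:

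- Section 7.6: "Subjects are to document all administered doses and missed doses in a medication diary for all study-required medication taken at home".
- Sections 7.1.2.2.2 and 7.1.2.3.2: the eCRF records the planned dose, the quantity administered and the reason for any dose change.
- Section 10.3.2.3.1: dose modifications, including withheld doses, are summarized with adverse-event and other reasons.

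On toxicity, both oral-drug sections state "Dose modifications are permitted in response to toxicity following the dose modification guideline tables". Tables 7-2 to 7-6 cover only carfilzomib and dexamethasone. Sections 7.4.1.4 and 7.4.1.5 leave toxicity changes in the oral drugs to the investigator and the labeling.

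**The concern.** A cycle is a 28-day unit in the same paragraph, so resuming with the next cycle means waiting for the next day 1. A subject who forgets the capsules on days 8 and 9 would go without the drug from day 8 to day 28, which is 21 days. With resumption on day 10, the days off would be days 8, 9 and 22-28, which is 9. Carfilzomib and dexamethasone keep to their own schedule meanwhile, so a triplet subject receives a doublet.

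Two things are at stake. One is treatment: an ordinary lapse costs more drug than the lapse itself. The other is measurement: describing adherence is part of the primary objective, and the cumulative dose proportion counts doses that the subject missed and doses that the rule then withheld in the same way.

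There is also a consistency risk. If the wording is a slip for the next scheduled dose, sites that follow the text and sites that follow common practice would handle the same lapse differently, across about 40 sites (Section 5.2.2).

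**Working it through.** **Inputs.** Both drugs are given once daily on days 1-21 of each 28-day cycle, lenalidomide at 25 mg and pomalidomide at 4 mg (Sections 7.1.2.2.2 and 7.1.2.3.2), for 12 cycles (Synopsis, Treatments). The denominator keeps skipped doses (Section 10.3.2.3.1). The plan states no intended cumulative dose or expected loss for these drugs, so there is no figure of its own to reproduce on this point. The SAP of 08 June 2018 predates the triplet arms and defines no dose measure for either drug.

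**Full course.** 21 x 12 = 252 doses. That is 252 x 25 = 6300 mg lenalidomide or 252 x 4 = 1008 mg pomalidomide.

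**Loss from one lapse.** Take a lapse of L days starting on day d, with d from 1 to 22 - L.

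- Resume at the next scheduled dose: L doses lost.
- Resume with the next cycle: 22 - d doses lost.
- Due to the rule alone: 22 - d - L.

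It is unclear whether one wholly missed day already triggers the rule, so L = 2 is used:

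| Start day | Lost under the rule | Share of 252 | Lost with next-dose resumption |
|---|---|---|---|
| 1 | 21 | 8.3% | 2 (0.8%) |
| 8 | 14 (350 mg lenalidomide or 56 mg pomalidomide) | 5.6% | 2 (0.8%) |
| 15 | 7 | 2.8% | 2 (0.8%) |
| 20 | 2 | 0.8% | 2 (0.8%) |

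**Average over start days** (all start days taken as equally likely, an assumption). The mean start day is (23 - L)/2, so the mean loss due to the rule is 22 - (23 - L)/2 - L = (21 - L)/2.

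- L = 2: 9.5/252 = 3.8 points
- L = 3: 9/252 = 3.6 points
- L = 5: 8/252 = 3.2 points
- L = 7: 7/252 = 2.8 points

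**Arm mean.** Lapse frequency is not in the documents. With k two-day lapses per subject over a full 12 cycles, the fall due to the rule is k x 9.5/252:

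- k = 0.25: 0.9 points
- k = 0.5: 1.9 points
- k = 1: 3.8 points

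**Scale.** Section 10.1 gives half-widths for a mean with n = 25. They reproduce as 1.96 x SD/5 = 2.0, 3.9 and 5.9 for SD 5, 10 and 15. They are stated for relative dose intensity, whereas the affected endpoint also counts every dose lost to early stopping.

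For a rough spread of that endpoint, take the 12-cycle completion rates p assumed in Section 10.1. Assume also that completers receive 100% and that non-completers stop uniformly over the course. The mean is then p + (1 - p)/2, and the variance is p + (1 - p)/3 minus the mean squared.

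| p | Mean | Variance | SD (points) | Half-width, 1.96 x SD/5 |
|---|---|---|---|---|
| 0.50 | 0.750 | 0.6667 - 0.5625 = 0.1042 | 32 | 12.7 |
| 0.75 | 0.875 | 0.8333 - 0.7656 = 0.0677 | 26 | 10.2 |
| 0.90 | 0.950 | 0.9333 - 0.9025 = 0.0308 | 18 | 6.9 |

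Even one lapse per subject (3.8 points) lies inside the narrowest of these.

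**The case against.** The strongest reply has four parts.

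- **The endpoint works as defined.** It is a gross measure of delivered dose that deliberately ignores why a dose was not given. A skip directed by the protocol lowers it just as a toxicity hold or early stop does. This stands: the definition is not broken.
- **The split may be recoverable.** A reader might infer from the diary wording in Section 7.6 that doses withheld under the rule cannot be told apart from doses the subject missed. The documents do not support that. The eCRF records planned dose, quantity and reason for dose change, and withheld doses are summarized with reasons. No specific category for rule-withheld doses appears, but the CRF categories are not in the documents, so the split is uncertain rather than absent.
- **The effect may be small.** A reader might set 0.9-3.8 points against the 2.0-5.9 in Section 10.1 and conclude that the rule rivals the planned precision. That is the wrong yardstick, because those half-widths belong to relative dose intensity. The lapse rates are also assumed, and the 8.3% is the extreme case of a day 1 lapse.
- **The rule has not been shown to be wrong.** Carfilzomib is a clinic infusion, and the labeling cited for the oral drugs is not in the documents. A missing reason is not proof of error. Nor do Sections 7.4.1.4 and 7.4.1.5 contradict the rule: they govern toxicity. The text does not say whether a toxicity hold also falls under the missed-dose rule.

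None of this changes the literal instruction or the doses it forfeits.

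**Conclusion.** The point holds. As written, both oral-drug sections turn a 2-day lapse into the loss of the rest of the 21-day block: 14 doses (5.6%) from day 8 instead of 2 (0.8%), and 9.5 extra doses (3.8 points) on average if start days are uniform. The loss falls on the lenalidomide and pomalidomide proportions in KRd and KPd. The Kd arm and the carfilzomib and dexamethasone proportions are untouched. The protocol does not say whether the proportion is reported per drug or combined.

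The per-lapse figures follow from the text. The arm-level figures rest on assumed lapse rates and full exposure, and are probably small next to the spread from early discontinuation. The study is descriptive, so no test or decision rule depends on them. The reason to act is the treatment lost after an ordinary lapse, plus an avoidable component in an adherence measure. The change should be made, although leaving it would not invalidate the study.

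**What to change.** In Section 7.1.2.2.2, keep the same-day sentence. Replace the sentence on longer lapses and the one pointing to the dose modification tables with:

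*A dose not taken on its scheduled day is not made up; dosing resumes with the next scheduled daily dose within days 1-21. Holds, reductions and restarts for toxicity follow Section 7.4.1.4 and the approved labeling.*

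Make the same change in Section 7.1.2.3.2, citing Section 7.4.1.5. This also settles the case of one wholly missed day and removes a pointer to tables that do not cover these drugs.

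If waiting for the next cycle is intended, state the reason and report doses skipped under the rule separately from doses the subject missed.

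**Cost.** The wording is two sentences in each of two sections. The change still needs a protocol amendment, which each site submits to its IRB and has approved where necessary, and re-consent if the consent form changes (Appendix 3). Sites must re-instruct subjects who take the capsules at home. Subjects treated before and after the change would follow different rules, so the report should note its date.

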#### 7.1.2.3 Pomalidomide

# 7.1.2.3.1 Prescribing Requirements

Pomalidomide, a non-Amgen non-investigational product, will also be used in this study for the KPd treatment arm. Pomalidomide should be administered in accordance with the POMALYST REMS® program of Celgene Corporation (http://www.pomalystrems.com/.) All physicians who prescribe pomalidomide for

research subjects assigned to the KPd arm of this study, and all research subjects enrolled on this study who are assigned to the KPd arm, must be registered in and comply with all requirements of the POMALYST REMS® program.

Females of childbearing potential (FCBP) must agree to monitoring for pregnancy. In addition, males and FCBP are subject to certain restrictions as detailed in Section 12.5 while receiving pomalidomide.

## 7.1.2.3.2 Dosage, Administration, and Schedule

Pomalidomide will be taken once-daily orally at a dose of 4 mg on days 1-21 of each 28-day cycle. Pomalidomide should be taken at home by the subject at about the same time each day. Pomalidomide capsules should be swallowed whole with water. The capsules should not be opened, broken, or chewed. If a planned dose is missed, it should be taken as soon as possible within the same calendar day and with a return to the regular schedule the following day. If a planned dose is missed for more than a calendar day, subjects should not make up doses, but should resume the dosing regimen on schedule with the next cycle. Dose modifications are permitted in response to toxicity following the dose modification guideline tables.

Protocol Number: 20170596

**Date:** 20 May 2019 **Page 54 of 132** 

The planned dose, quantity administered, start date, start time, and reason for dose change are to be recorded on each subject's eCRF.

## 7.1.3 Medical Devices

No investigational medical devices will be used in this study.

Other non-investigational medical devices may be used in the conduct of this study as part of standard care.

Non-investigational medical devices (eg, syringes, sterile needles), that are commercially available are not usually provided or reimbursed by Amgen (except, for example, if required by local regulation). The investigator will be responsible for obtaining supplies of these devices.

# 7.1.4 Other Protocol-required Therapies

Protocol-required, suggested, or permitted supportive therapies listed below are commercially available and will not be provided or reimbursed by Amgen (except if required by local regulation). The investigator will be responsible for obtaining supplies of these protocol-required therapies.

Additional details regarding these protocol-required therapies are provided in the IPIM.

## 7.1.4.1 Antiviral Prophylaxis

An antiviral is a required concomitant medication for the duration of treatment with carfilzomib. Acyclovir (eg, 400 mg orally 3 times a day, or 800 mg orally 2 times a day, or per institutional standards), famcyclovir (eg, 125 mg orally given for 3 days, 2 times a day, or per institutional standards), or valacyclovir (eg, 500 mg orally 2 times a day, or per institutional standards), dose adjustments for renal function where appropriate, initiated within 1 week of the first dose should continue for the duration of treatment with carfilzomib.

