# 7.1.1.2 Dosage, Administration, and Schedule

For all treatment arms, carfilzomib will be administered at 20 mg/m² on days 1 and 2 of the first cycle (see Table 7-1). For subjects in the Kd arm, carfilzomib will be administered at 56 mg/m² on days 8, 9, 15, and 16 of the first cycle, and then on days 1, 2, 8, 9, 15, and 16 in cycle 2. Starting with cycle 3 through cycle 12, carfilzomib will be administered at 70 mg/m² on days 1, 8, and 15 of each 28-day cycle. For subjects in the KRd and KPd arms, carfilzomib will be administered at 27 mg/m² on days 8, 9, 15, and 16 of the first cycle, and then on days 1, 2, 8, 9, 15, and 16 in cycle 2. Starting with cycle 3 through cycle 12, carfilzomib will be administered at 56 mg/m² on days 1, 8, and 15 of each 28-day cycle.

Protocol Number: 20170596

**Date:** 20 May 2019 Page 50 of 132

At the time of implementation of protocol amendment 3, subjects previously enrolled may have completed more than 2 but less than 6 cycles of twice weekly carfilzomib dosing on the Kd arm as per protocol amendment 2. These subjects should complete the dosing regimen as per protocol amendment 2, (ie, 6 cycles of twice weekly dosing for carfilzomib [Kd 56 mg/m²] transitioning to once weekly dosing for carfilzomib [Kd 70 mg/m²], starting with cycle 7). For these subjects, the schedule of activities outlined per Table 2-1 for cycles 1 and 2 will continue for cycles 1 through 6. At the start of cycle 7, these subjects will then follow the schedule of activities as outlined per Table 2-1 cycles 3 through 12. In addition, the starting nominal dose of carfilzomib on day 1 cycle 7 (which is the initiation of the once weekly carfilzomib dosing for these subjects) should be reduced by the same number of dose levels and same percentage dose reduction as it was reduced to during cycle 6 (which is the twice weekly carfilzomib dosing). Dexamethasone will be administered at a dose of 20 mg once daily on days 1, 2, 8, 9, 15, 16, 22, and 23 cycles 1 through 6 and at a dose of 40 mg once daily on days 1, 8, 15 for the Kd arm for cycles 7 through 12 for these subjects.

All doses should be administered on the scheduled day  $\pm$  2 days, and the day 8 and 15 doses should have at least a 5-day treatment-free interval. The starting dose should be modified for chronic mild hepatic insufficiency per Section 7.1.1.2.1.

Table 7-1. Carfilzomib Dosage

Cycle 1	Cycle 2	Cycles 3-12		
Kd Arm				

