**Date:** 20 May 2019 **Page 67 of 132** 

Concomitant therapies are to be collected from 30 days prior to enrollment through the end of study.

For concomitant therapies, collect therapy name, indication, dose, unit, frequency, start date and stop date.

Concomitant medications used prophylactically should be described as such on the designated eCRF. Blood and blood products are not considered concomitant medications and must be recorded on the appropriate eCRF.

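### Section 7.1.4.1 requires antiviral cover for as long as carfilzomib is given, but its famciclovir example is a 3-day course (minor)

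*Protocol*

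**What the plan says.** Protocol Section 7.1.4.1 opens with the rule: "An antiviral is a required concomitant medication for the duration of treatment with carfilzomib". It then names three agents, each with an example regimen and the option of following institutional practice:

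- Acyclovir, 400 mg three times a day or 800 mg twice a day, with no day limit.
- Famciclovir: "famcyclovir (eg, 125 mg orally given for 3 days, 2 times a day, or per institutional standards").
- Valacyclovir: "valacyclovir (eg, 500 mg orally 2 times a day, or per institutional standards"), again with no day limit.

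The sentence that lists them ends with an instruction covering all three: "initiated within 1 week of the first dose should continue for the duration of treatment with carfilzomib".

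The length of carfilzomib treatment comes from Section 7.1.1.2. Cycle 1 has six doses, on days 1, 2, 8, 9, 15 and 16. Cycle 2 has the same pattern ("and then on days 1, 2, 8, 9, 15, and 16 in cycle 2"). Cycles 3 to 12 have three doses each, "on days 1, 8, and 15 of each 28-day cycle". Some Kd subjects enrolled earlier stay on a longer twice-weekly phase of six cycles: "These subjects should complete the dosing regimen as per protocol amendment 2".

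**The concern.** The paragraph states its duration rule twice and then gives, for one of the three agents, an example that stops after 3 days. A site that prescribed from the example as printed would end a required safety measure in the first cycle or so while carfilzomib went on for up to a year.

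This is an operative prescribing instruction. Under Section 7.1.4 the investigator obtains these drugs, so the printed regimen may be what a site writes on the order. Section 3.3.3.1.14 lists herpes zoster as an important potential risk of carfilzomib, with a pooled subject incidence of 2.9% and serious events below 0.1%. It gives prophylaxis as the means of reducing reactivation.

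**Working it through.** There is no plan figure to reproduce. The check compares the wording and then counts how much of the planned treatment the example would cover.

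**Wording.** The rule at the start and the instruction at the end both set the duration as the whole of carfilzomib treatment. Two of the three examples are open-ended and fit. Only the famciclovir example carries a stop.

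**Inputs** (Section 7.1.1.2): 28-day cycles, 12 cycles, six carfilzomib doses per twice-weekly cycle, three per once-weekly cycle, last dose of a once-weekly cycle on day 15.

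**Treatment length**

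- Twelve full cycles: 12 × 28 = 336 days.
- Last planned carfilzomib dose, cycle 12 day 15: 11 × 28 + 15 = day 323.

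**Planned carfilzomib doses**

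- Current schedule: 2 × 6 + 10 × 3 = 42.
- Kd subjects finishing the amendment 2 schedule: 6 × 6 + 6 × 3 = 54.

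**Cover from a 3-day course started on day 1**

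- Days 1 to 3 contain the day 1 and day 2 doses, so 2 doses.
- Current schedule: 2/42 = 4.8%, leaving 40 doses.
- Amendment 2 schedule: 2/54 = 3.7%, leaving 52 doses.
- By time to the last dose: 3/323 = 0.9% of days.

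**Does the start day matter?** The protocol allows a start within a week of the first dose. The dose days in cycle 1 are 1, 2, 8, 9, 15 and 16. A course covers its start day and the next two days:

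| Start day | 1 | 2 | 3 | 4 | 5 | 6 | 7 | 8 |
|---|---|---|---|---|---|---|---|---|
| Doses covered | 2 | 1 | 0 | 0 | 0 | 1 | 2 | 2 |

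The maximum is 2, whichever day is chosen.

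**A more generous reading.** If the course were repeated every cycle, which the text does not say, it would cover 12 × 3 = 36 of 336 days (10.7%). That does not meet the rule either.

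**The case against.** The strongest reply is that the paragraph corrects itself. The 3-day phrase sits inside an illustration that also offers an institutional regimen, and the clause closing the sentence tells sites to continue whichever agent they choose. To stop on day 3, a site would have to treat an example as binding and ignore the rule on either side of it. The other two agents are available without any day limit. The percentages above therefore describe a hypothetical subject, and the Kd subject on the amendment 2 schedule is more remote still.

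Three further points can be made. Section 7.1.4 refers to additional detail in the Investigational Product Instruction Manual, which is not among the documents and may settle the matter. Section 7.8.2 requires the relevant data ("For concomitant therapies, collect therapy name, indication, dose, unit, frequency, start date and stop date"), and the Data Quality Assurance part of Appendix 3 (Section 12.3) provides for ongoing source data verification, so an early stop could be noticed and prophylaxis resumed. Finally, the zoster rates in Section 3.3.3.1.14 are low, and that section only asks that prophylaxis be considered.

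Most of this stands, and it is why the point is minor. It does not make the printed example comply: the alternatives let a site avoid the example, but the example itself still breaks the rule. Nor can the low pooled rates show that stopping early is harmless, because the documents do not say how much prophylaxis those subjects received.

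**Conclusion.** The inconsistency is real and confined to one example in one paragraph. The intended design, continuous prophylaxis, is clear.

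For a subject treated exactly as the example is printed, at most 2 of 42 planned carfilzomib doses would be covered, or 2 of 54 on the amendment 2 schedule. These counts assume 12 full cycles on nominal days. The number of such subjects is unknown and may be zero, so the figures measure how far the example falls short of the rule. They are not an estimate of harm in the trial. No endpoint, analysis set, analysis or sample size depends on this wording. Severity is minor; confidence that the text conflicts is high.

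**What to change.** In Section 7.1.4.1, delete the four words in the famciclovir example that limit it to 3 days. The example then matches the other two agents and the rule around it.

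At the same time, ask the clinical team to confirm or replace 125 mg twice daily as a continuous prophylactic regimen. The dose was printed with a short course, and the documents cannot show whether it is the one intended for long-term use. This is a secondary request and does not imply that the dose is wrong.

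The cost is a four-word deletion and one dose check. There are no new visits, procedures or data.
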